**8.11.2. Secondary Efficacy Variable: Investigator's global assessment**

The Investigator's Global Assessment score is an ordered categorical value ranging from 0 (Clear) to 4 (Severe). The assessment is obtained at each visit. Investigator's Global Assessment score will be summarized for each treatment group and at each visit using the median, minimum, maximum and frequency distributions. Percent Change from baseline will be summarized for each follow-up visit. The comparison between the two treatments will be based on the difference for each subject between each visit including the endpoint visit, and the baseline visit. The van Elteren test, stratified by study center, as defined for the primary efficacy variable will be used for the analysis of IGA. Ordinal logistic regression models of the IGA, parameterized in the same manner as the ANCOVA models for the primary efficacy variable, will be used in an exploratory analysis of the impact of treatment on IGA scores.

**8.11.3. Secondary Efficacy Variable: Treatment responders**

Treatment responders will be defined at each visit and at endpoint as subjects who have either (1) two ordinal or more reductions in the Investigator's Global Assessment (IGA) or (2) an IGA score of 0 or 1.

Treatment response (yes/no) is a dichotomous binomial variable. Treatment response will be summarized for each treatment group and at each visit using frequency distributions. At each visit, these scores will be analyzed using a Fisher's exact test supplemented by a Mantel-Haenszel analysis stratified by Investigator. The Breslow-Day test will be used to test the homogeneity of the treatment responder effect among investigators. The analysis of treatment success at endpoint visit is the primary responder analysis.

**8.11.4. Secondary Efficacy Variable: Individual lesion counts**

As ancillary efficacy parameters, papules, pustule, and nodule counts will be summarized for each treatment group and at each visit using mean, standard deviation, median, minimum, and maximum. Change from baseline for papule, pustule, nodule, and papule plus pustule counts will be analyzed at each post randomization visit using the same parametric or non-parametric analysis as was used in the primary efficacy variable (total inflammatory lesions).

**8.11.5. Subgroup analyses**

Subgroup analyses including but not limited to race, age and sex will be performed for exploratory purposes on all secondary efficacy variables for the MITT population, provided adequate sample sizes are available in potential subgroups. In addition, the analyses performed on the PP population are considered exploratory.

**8.12. Safety Analyses**

Safety analyses will be performed on the safety population. The assessment of safety will be based on the summary of AEs, clinical laboratory sampling local tolerability assessment and vital signs.

Safety assessments of continuous variables will be summarized by descriptive statistics (n, mean, standard deviation, median, minimum and maximum), and categorical variables will be summarized using the count and percentage of subjects in each category.

**8.12.1. Adverse Events**

Verbatim terms for AEs reported during the study will be mapped to their corresponding thesaurus terms (preferred term and system organ class) from the Medical Dictionary for Regulatory Activities (MedDRA) coding dictionary, version 21.0. Summaries will be made

using the assigned preferred terms, and will be based on the number and percentage of subjects having at least one occurrence of the following:

- Any AE during the study;
- An AE within each system organ class;
- An individual AE (based on the preferred term).

Analysis will include frequencies and proportions of patients reporting AEs using the preferred terms and system organ class. Separate summaries of AEs with a suspected relationship to study medication (as reported by the Investigator) and by severity will be prepared. If applicable, the number of deaths and serious adverse events (SAEs) will also be presented, and events leading to discontinuation from the study will be listed and tabulated.

All AEs will be presented in a by-subject listing.

#### **8.12.2. Local tolerability assessment (LTA)**

Investigator Assessment: Assessments will be tabulated by n (%) within each category at each applicable visit and timepoint.

Subject Assessment: Assessments will be tabulated by n (%) within each category at each applicable visit and timepoint.

The data on local tolerability will be presented in a listing.

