3. STUDY OBJECTIVES

The main objective of this study is to evaluate the safety, tolerability and efficacy of ACU-D1 Ointment [REDACTED] when applied twice daily for 12 weeks to papulopustular (Type-2) rosacea (acne rosacea) of the face.

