4.3. Inclusion Criteria

To be eligible for enrollment at Visit 1 the subject must fulfill all the following inclusion criteria:

1. Subject is at least 18 years of age
2. Subject has a clinical diagnosis of stable papulopustular rosacea (type-2)
3. Subject has a total of ≥ 10 and ≤ 40 inflammatory lesions (papules, pustules and nodules) on the face
4. Subject has a ≤ 2 nodules on the face
5. Subject has an Investigator's Global Assessment score of ≥ 3
6. If the subject is a woman of childbearing potential, she has a negative urine pregnancy test and agrees to use an approved effective method of birth control for the duration of the study
7. Subject is non-pregnant and non-lactating
8. Subject is in good general health and free of any known disease state or physical condition which, in the investigator's opinion, might impair evaluation of rosacea or which exposes the subject to an unacceptable risk by study participation
9. Subject is willing and able to follow all study instructions and to attend all study visits
10. Subject is able to comprehend and willing to sign an Informed Consent Form.

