6.1.2. Investigator's global assessment (IGA)

The IGA is the investigator's assessment of the average overall severity of rosacea on the subject's face at a particular point in time. The investigator should NOT refer to any other assessments to assist with these assessments.

At Visits 1-7 the investigator will assess the rosacea on each subject's face and report the one integer that best describes the average overall severity using the scale below:

Investigator's Global Assessment	
Grade	Descriptor
0	Clear: No papules or pustules, no nodules, none or barely perceptible erythema
1	Near Clear: Very few (≤ 3) papules and/or pustules, no nodules, very mild erythema
2	Mild: Few papules and pustules present, no nodules, mild erythema
3	Moderate: Several papules and pustules are the predominant feature, ≤ 2 nodules may be present, moderate erythema
4	Severe: Numerous papules and pustules, multiple nodules may be present, severe erythema

At Visit 1, to be enrolled and at Visit 2, to be randomized, the subject must have an IGA grade of ≥ 3 (Moderate).

At Visit 2 the IGA must be completed prior to the start of the first study medication application.

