6.2.2. Local tolerability assessment (LTA)

The LTA is the investigator's assessment of the average overall severity of signs and the subject's assessment of the average overall severity of symptoms associated with irritation on the treated area. The investigator and subject must NOT refer to any other evaluation to assist with these assessments. This is not a comparison with the assessment at any other time point.

LTA Signs (assessed by the investigator):

- Erythema
- Scaling/dryness.

LTA symptoms (assessed by the subject):

- Stinging
- Burning
- Pruritus (itch).

At Visits 2-7, the investigator and the subject will evaluate the LTA signs and the LTA symptoms respectively.

The investigator will assess the LTA signs as follows:

- At Visit 2:
 - Prior to the first study medication application
 - 20 (\pm 4) minutes after the Application Completion Time.
- At Visits 3-7.

The subject will assess the LTA symptoms as follows:

- At Visit 2:
 - Prior to the first study medication application report the LTA for each symptom over the previous 24 hours
 - 10 (\pm 4) minutes after the Application Completion Time, report the LTA for each symptom since the Application Completion Time.
- At Visits 3-7:
 - Report the LTA for each symptom over the previous 24 hours.

The investigator, for the signs, should report the one integer that best describes the average overall severity on the face using the scales below:

Local Tolerability Assessment - Erythema	
Grade	Descriptor
0	Clear: No erythema present
1	Mild: Slight erythema
2	Moderate: Definite erythema
3	Severe: Marked, fiery erythema

Local Tolerability Assessment - Dryness/Scaling	
Grade	Descriptor
0	Clear: No signs of dryness or scaling
1	Mild: Slight roughness (may be more easily felt than seen), barely perceptible scaling
2	Moderate: Moderate roughness, definite scaling
3	Severe: Marked roughness, heavy scaling

The subject, for the symptoms, should report the one integer that best describes the average overall severity on the face using the scales below:

Local Tolerability Assessment - Stinging	
Grade	Descriptor
0	Clear: No stinging
1	Mild: Slight tingling, not bothersome
2	Moderate: Definite tingling, slightly bothersome
3	Severe: Intense stinging, bothersome and/or uncomfortable

Local Tolerability Assessment - Burning	
Grade	Descriptor
0	Clear: No burning
1	Mild: Slight warmth, not bothersome
2	Moderate: Definite warmth, slightly bothersome

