7.1. Definitions

7.1.1. Adverse events (AE)

An AE is any untoward medical occurrence in a patient or clinical investigation subject administered a pharmaceutical product and which does not necessarily have a causal relationship with this treatment. An AE can therefore be any unfavorable and unintended sign or symptom associated with the use of an investigational product (including an abnormal laboratory finding), whether or not related to the investigational product.

Thus any new, clinically relevant worsening of an existing sign, symptom or disease, should be considered an AE.

Worsening of the Lesion Count, IGA or LTA should be reported as an AE only if the use of the study medication is interrupted or discontinued or other therapy is required to manage the event.

Every new episode or clinically relevant worsening of a chronic condition (*e.g.*, headaches, allergies, depression, and hypertension) should be reported as a separate AE, even if the condition is reported in the subject's medical history.

The investigator should, when certain, report a diagnosis rather than the signs, symptoms or clinically relevant abnormal laboratory values associated with the AE. Otherwise, signs, symptoms or abnormal laboratory values may be used to describe the AE.

An abnormality discovered (*e.g.*, clinically relevant laboratory abnormalities), prior to the first study medication application, should be reported as medical history, not as an AE.

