#### **8.12.3. Vital Signs**

At Visits 1, 2 and 7 vital signs to include Body temperature, Pulse rate, Respiration rate, Blood pressure (systolic and diastolic) after the subject sits quietly for at least 5 minutes, Height (at Visit 1 only), Weight (at Visit 1 only) will be measured. The observed and change from baseline scores will be summarized using descriptive statistics. Height and weight will be presented in the Demography table, since they are measured only at Visit 1.

The vital sign data will be presented in a listing.

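### SAP 8.12.2 tabulates LTA grades visit by visit but plans no summary of within-subject change from the Visit 2 pre-application score, and the erythema item overlaps with the disease

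*SAP*

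**What the plan says.** Protocol 3 makes tolerability part of the single objective: "The main objective of this study is to evaluate the safety, tolerability and efficacy of ACU-D1 Ointment".

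Protocol 6.2.2 defines five LTA items, each graded 0 to 3. The investigator grades erythema and scaling/dryness; the subject grades stinging, burning and pruritus. Each is a static score. All five are taken before the first application at Visit 2, again shortly afterwards (symptoms at about 10 minutes, signs at about 20), and at Visits 3 to 7. SAP 8.5.1 makes Visit 2 the baseline.

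For both raters SAP 8.12.2 plans the same summary: "Assessments will be tabulated by n (%) within each category at each applicable visit and timepoint". It adds a listing. Neither document plans a shift, change, worst-grade or any-worsening summary of LTA. For vital signs, SAP 8.12.3 does plan change: "The observed and change from baseline scores will be summarized using descriptive statistics".

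Protocol 7.1.1 limits what reaches the adverse event tables: "Worsening of the Lesion Count, IGA or LTA should be reported as an AE only if the use of the study medication is interrupted". The same sentence also admits worsening that leads to stopping the medication or to a need for further treatment.

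On erythema, Protocol 4.3 requires this for entry: "Subject has an Investigator's Global Assessment score of ≥ 3". The IGA grade 3 descriptor in Protocol 6.1.2 reads "Several papules and pustules are the predominant feature, ≤ 2 nodules may be present, moderate erythema", and grade 4 names severe erythema. LTA grades 2 and 3 for erythema are "Moderate: Definite erythema" and "Severe: Marked, fiery erythema".

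**The concern.** A table of grades at each visit shows how the group is distributed, not what happened to each subject. Subjects who worsen and subjects who improve cancel out, and irritation that comes and goes in different subjects at different visits never adds up to a cumulative count. The question that a tolerability objective asks is how many subjects got worse on treatment, by item and arm. The planned tables cannot answer it, although the data needed are collected. The adverse event tables do not fill the gap: a subject who goes from no burning to moderate burning, stays on treatment and needs no other therapy does not enter them.

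Erythema raises a second question. It is scored as a sign of irritation, but it is also a feature of the disease that the IGA grades on the same face, and nothing in the LTA descriptors separates the two sources of redness. If active treatment reduces disease redness more than vehicle does, the erythema item would tend to favour active whatever irritation is present.

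**Working it through.** The documents give no LTA rate, threshold or power figure, so there is no stated number to reproduce. Only the arm sizes come from the documents (24 active and 12 vehicle; Protocol 4.1, SAP 4). All grade counts and rates below are assumptions chosen to show the range.

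**1. What per-visit counts determine.** Fix the counts at baseline and at one follow-up visit in grades 0/1/2/3. Over all 4 × 4 shift tables with those margins, find the smallest and largest number of subjects whose follow-up grade is higher than their baseline grade.

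| Arm | Baseline 0/1/2/3 | Follow-up 0/1/2/3 | Worsened, min to max |
|---|---|---|---|
| Active, 24 | 0/0/18/6 | 0/0/18/6 | 0 to 6 (0% to 25%) |
| Active, 24 | 0/0/18/6 | 4/10/6/4 | 0 to 4 (0% to 17%) |
| Active, 24 | 0/6/12/6 | 4/10/6/4 | 0 to 10 (0% to 42%) |
| Vehicle, 12 | 0/0/9/3 | 1/4/5/2 | 0 to 2 (0% to 17%) |

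The first row can be checked by hand. If nobody moves, 0 worsen. If 6 go from grade 2 to 3 and 6 go from 3 to 2, then 6/24 = 25% worsen, and the table is the same. In the third row, 6 can go from grade 1 to 2 and 4 from grade 2 to 3, giving 10/24 = 42% in a group that improves overall. The argument applies to any of the five items.

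**2. Overlap of erythema with disease.** Suppose a share i gains one grade from irritation and, independently, a share d loses one grade of disease redness. Net visible worsening is i × (1 − d). With i = 20% assumed, 24 × 0.20 = 4.8 subjects are irritated. The number who show a higher erythema grade is then:

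- d = 0: 4.8
- d = 30%: 24 × 0.20 × 0.70 = 3.4
- d = 50%: 24 × 0.20 × 0.50 = 2.4
- d = 70%: 24 × 0.20 × 0.30 = 1.4

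The comparison between arms is distorted only if d differs between them. A shift table resolves step 1 but not this step, because the shift in erythema carries the same mixture.

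**3. Precision of a worsening proportion** (exact Clopper-Pearson 95% limits):

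- 0/24: upper limit 14.2%
- 3/24 = 12.5%: 2.7% to 32.4%
- 0/12: upper limit 26.5%

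The added summary would be descriptive only.

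**The case against.** The strongest reply is that this is a pilot with descriptive safety, and that the SAP follows its own rule: SAP 8.12 gives categorical safety variables counts and percentages, and 8.12.2 does that. Vital signs are continuous, so summarizing their change is not an inconsistency. This stands. The contrast shows only that within-subject change was thought of elsewhere.

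A reader might infer that individual worsening is hidden. The documents do not support that. SAP 8.12.2 plans an LTA listing, and with about 36 subjects worsening can be counted by hand. It is unsummarized, not unavailable. What remains is that a hand count has no pre-specified definition of worsening.

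A reader might also infer that entry requires moderate erythema, so that most subjects start near the top of the LTA scale. Protocol 4.3 has no erythema criterion, the IGA is a best-fit overall grade, and nothing maps it to LTA grades. High baseline LTA erythema is plausible but inferred.

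Nor does it follow that an effective arm will look well tolerated on the LTA as a whole. Scaling/dryness, stinging, burning and pruritus are not IGA features, and the Visit 2 post-application readings come too early for disease response. The protocol proposes benefit for inflammatory lesions and does not say that ACU-D1 lowers erythema. The vehicle arm controls for natural course, though not for a difference between arms in disease redness.

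Intolerance with consequences is captured elsewhere: application changes are recorded (Protocol 5.6.8), and reasons for discontinuation and events leading to it are tabulated (SAP 8.6, 8.12.1). Worsening without such consequences is not. Finally, SAP 9 places the table shells in a separate document, which might contain a shift table; the SAP text does not plan one.

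**Conclusion.** The gap is real but limited. For an outcome named in the main objective, with a pre-application baseline in hand, the SAP plans no summary of within-subject change, and the adverse event rule leaves out worsening that leads to no interruption, discontinuation or other therapy. Under the assumed counts, the planned tables leave the number worsened open by as much as 0 to 10 of 24. The assumptions set the width of that range; that per-visit counts generally leave the number open does not depend on them.

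The erythema point is conditional. LTA erythema may partly reflect rosacea, and it could understate irritation if active lowers disease redness more than vehicle. Neither the baseline LTA erythema grades nor the size of any such effect is given, so no bias can be claimed as established. It concerns one item of five.

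A reader might conclude that erythema should be set aside and tolerability judged on the other four items. The documents do not support this: Protocol 6.2.2 names erythema as a sign of irritation, and removing it could itself understate irritation. No primary analysis, error rate or efficacy decision is affected.

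**What to change.** In SAP 8.12.2 add, by arm and for each of the five LTA items:

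1. a shift table from the Visit 2 pre-application grade to the worst grade over Visits 3-6 (Visit 7 is left out because it follows two weeks off treatment);
2. the number and percent of subjects with a worsening of at least one grade at any of Visits 3-6;
3. the Visit 2 pre- to post-application shift. For symptoms, note that the recall period differs: the previous 24 hours before application, and the time since application afterwards.

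State that erythema is to be read alongside the other four items because it overlaps with disease erythema, and keep it in the tolerability conclusion. Make the change before unblinding, as SAP 8 requires for amendments. If the table shells already hold such tables, bring the SAP text into line with them.

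The cost is a few descriptive tables from data already collected, with no new assessments. Precision will be low: even 0/24 leaves an upper 95% limit of about 14%. Some counted worsening will be ordinary fluctuation, which the vehicle arm helps to gauge. The shift tables do not remove the overlap of erythema with disease, which is why the interpretive statement is needed as well.

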#### **8.12.3. Vital Signs**

At Visits 1, 2 and 7 vital signs to include Body temperature, Pulse rate, Respiration rate, Blood pressure (systolic and diastolic) after the subject sits quietly for at least 5 minutes, Height (at Visit 1 only), Weight (at Visit 1 only) will be measured. The observed and change from baseline scores will be summarized using descriptive statistics. Height and weight will be presented in the Demography table, since they are measured only at Visit 1.

The vital sign data will be presented in a listing.

#### **8.12.4. Clinical Laboratory Assessment**

At Visits 1 and 6 non-fasting blood samples will be collected for analysis including chemistry panel, complete blood count and urinalysis.

The clinical laboratory assessments will be presented in a listing.

#### **8.12.5. Urine Pregnancy test**

The urine pregnancy tests will be presented in a listing.

### **9. LIST OF SUMMARY TABLES AND LISTINGS**

Table shells and list of listings are in a separate document.
